## 6 Donors

Additional cells sufficient for a DLI must be available, or the previous donor must be willing to donate again. The required total dose of CD3 cells ( $\times 10^8$ ) per recipient's body weight in kg for 4 DLI procedures is 66, 16.6, and 1.66 for matched sibling, matched unrelated, haploidentical donors, respectively. Donor selection will be in compliance with 21 CFR Part 1271 and institutional guidelines. If requesting additional collections from the previous donor, donor assessment and consent process will occur per institutional SOPs for related donors or per National Marrow Donor Program (BeTheMatch.org) SOPs for matched unrelated donors, in the apheresis center or similar donor facility. No study-specific consent is needed from donors.

For affiliates: affiliate sites may use their institutional guidelines in evaluating related donor eligibility. Matched unrelated donors will be evaluated according to institutional and/or National Marrow Donor Program guidelines. The current study does not determine any donor-specific eligibility.

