## Schema

\*DLI dose escalation algorithm

	MSD	MUD	Haploididential
DLI #1, $\times 10^8$ CD3/kg	0.1-1	0.05-0.5	0.01-0.1
DLI #2, $\times 10^8$ CD3/kg	0.5-5	0.1-1	0.05-0.5
DLI #3, $\times 10^8$ CD3/kg	1-10	0.5-5	0.1-1
DLI #4, $\times 10^8$ CD3/kg	5-50	1-10	0.5-5

DLI: Donor lymphocyte infusion; MSD: Matched sibling donor; MUD: Matched unrelated donor

\*\*If CR is achieved after cycle 2, patients will be switched to a 5 day schedule.

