#### 4 Study Design

This is a multi-center, single-arm, open-label, phase II trial for the frontline treatment of relapsed AML or MDS following allo-HCT.

Eligible subjects will receive up to 4 cycles of combined modality treatment. The number of cycles depends on response, toxicity, and the remaining cell dose.

Cycles include:

- 10 days of decitabine 20 mg/m^2 IV daily; or, alternatively, per institution, physician, or patient preference on a 5-2-5 schedule with no weekend infusion. If a CR is achieved after 2 cycles using the 10-day schedule, subsequent cycles will change to a 5-day schedule.
- Starting with decitabine and continuing for up to 6 months after the end of the last cycle, patients will receive ruxolitinib 5 mg twice daily orally.
- DLI from the original donor will be infused within 10 days after the last dose of decitabine in each cycle.

Patients will be screened for ongoing eligibility before each subsequent cycle of therapy. Patients with disease progression, new GVHD (except grade I acute GVHD), prolongation of the most recent cycle to more than 8 weeks (for any reason), or inadequate cell dose for further DLI will not receive further treatment on study. The DLI dose in each cycle will be

determined according to a donor-dependent dose-escalation algorithm (schema). If the collected cell dose in the DLI is less than the target dose, the patient will receive those collected cells and subsequently removed from further treatment cycles. These subjects will continue to be followed per protocol.

The expected duration of treatment for each subject is 4 cycles of treatment, each lasting 4-8 weeks.

Approximately 34 subjects will be enrolled (32 evaluable) over a period of 24 months, with an additional 12 months of follow up.

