### 5.1 Inclusion Criteria:

- 5.1.1** Age  $\geq$ 12 years
- 5.1.2** Have undergone first allo-HCT from a 6/6 matched sibling donor, 8/8 matched unrelated donor, or an HLA haploidentical donor.
- 5.1.3** History of AML or MDS for which allo-HCT was performed. Overlap MPN/MDS is included.
- 5.1.4** Untreated relapse of the underlying malignancy as defined by >5% of malignant blasts (by morphology and/or flow cytometry) in the bone marrow, or myeloid sarcoma.
- 5.1.5** Additional cells sufficient for the first DLI available from the same donor, or the donor must be willing to donate. Both G-CSF mobilized and unmobilized products are allowed and the choice is at the discretion of the treating physician.
- 5.1.6** Partial (or better) engraftment from the bone marrow showing relapse, defined as >50% donor chimerism on non-split RFLP. Patients with chimerism of 25-50% may be enrolled with approval of the site PI and Sponsor/Investigator.

**5.1.7** Karnofsky performance status  $\geq$  50% ([appendix I](#))

**5.1.8** Adequate organ function within 14 days of study registration defined as:

- Total bilirubin  $< 1.5 \times$  upper limit of institutional normal, unless a diagnosis of Gilbert's disease
- AST/ALT  $\leq 2.5 \times$  upper limit of institutional normal
- Creatinine clearance  $\geq 40$  mL/minute as calculated by the Cockcroft-Gault formula. Cockcroft-Gault CrCl =  $(140\text{-age}) * (\text{Wt in kg}) * (0.85 \text{ if female}) / (72 * \text{Cr})$ .

**5.1.9** Peripheral white blood cell count  $< 50 \times 10^9/\text{L}$ . The use of hydroxyurea for cytoreduction is allowed and may continue until cycle 2 day 1

**5.1.10** Subjects and spouse/partner who are of childbearing potential must be using highly effective contraception consisting of 2 forms of birth control (at least 1 of which must be a barrier method) starting at Screening and continuing through the entire study (for at least 3 months after the last dose of ruxolitinib if study treatment is stopped early or subject withdraws consent). Highly effective contraception is defined as:

- Established use of oral, injected or implanted hormonal methods of contraception.
- Placement of an intrauterine device or intrauterine system.
- Double barrier methods of contraception: condom or occlusive cap (diaphragm or cervical/vault caps) with spermicidal foam/gel/film/cream/suppository (double barrier method will count as 2 forms of contraception).

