## 8.2 DLI

Within 10 days after the last dose of decitabine in each cycle, a DLI product from the previous donor (either remaining from the original transplant unit, or a new unit) will be infused. Donor lymphocytes will be obtained by lymphapheresis from the same allogeneic donor used for transplantation. For local related donors, lymphocyte collections will be performed using standard automated mononuclear cell collection techniques by the University of Minnesota Blood Bank or study affiliate site's institutional guidelines. For unrelated donors or non-local related donors, the lymphocyte collection will be performed at an outside facility according to procedures set by the National Marrow Donor Program. If the collection is non-local, coordination for the timing of the cell collection and the ability to transport the cells to the study site is required. Similarly, for local related donors, the timing of collection (same day as infusion vs. cryopreserved) is according to the collaborating centers' institutional guidelines.

The duration of DLI will be determined according to the collaborating centers' institutional guidelines. DLI will be administered according to a donor-dependent dose-escalation algorithm ([Table 4](#)). In the absence of new GVHD (any grade), the dose of DLI for the next cycle will be higher than the previous cycle. Otherwise, the dose will remain the same. DLI will be given without adding immunosuppressive medications and without conditioning. Addition of immunosuppressive medications as indicated to treat grade I acute GVHD or other non-GVHD steroid-responsive conditions is allowed.

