**Table 4: DLI dose escalation algorithm**

	MSD	MUD	Haploidentical
DLI #1, $\times 10^8$ CD3/kg	0.1-1	0.05-0.5	0.01-0.1
DLI #2, $\times 10^8$ CD3/kg	0.5-5	0.1-1	0.05-0.5
DLI #3, $\times 10^8$ CD3/kg	1-10	0.5-5	0.1-1
DLI #4, $\times 10^8$ CD3/kg	5-50	1-10	0.5-5

DLI: Donor lymphocyte infusion; MSD: Matched sibling donor; MUD: Matched unrelated donor

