#### **Inclusion Criteria (on or before Day 1 of Cycles 2-4)**

Patients must meet the following criteria within 7 days prior to day 1 of cycles 2-4 unless otherwise noted.

- 8.5.1** Stable disease or better on bone marrow biopsy within 7 days before cycle 3 (required) and cycles 2 and 4 (if performed). A bone marrow biopsy before cycles 2 and 4 is not required.
- 8.5.2** Additional cells available from the same donor used for the first DLI or the donor willing to donate ([Table 4](#)). This dose will allow for at least one more DLI. Both G-CSF mobilized and unmobilized products are allowed. If a sufficient number of cells for the next DLI is not available, patients will not receive further treatment on study.
- 8.5.3** Adequate organ function:
  - Total bilirubin < 1.5 x upper limit of institutional normal, unless a diagnosis of Gilbert's disease
  - AST/ALT < 2.5 x upper limit of institutional normal
  - Creatinine clearance  $\geq$  40 mL/minute within 3 days prior to day 1, as calculated by the Cockcroft-Gault formula. Cockcroft-Gault CrCl =  $(140 - \text{age}) * (\text{Wt in kg}) * (0.85 \text{ if female}) / (72 * \text{Cr})$ .
- 8.5.4** Peripheral white blood cell count  $< 50 \times 10^9 / \text{L}$  within 3 days prior to day 1. The use of hydroxyurea is allowed and may continue until day 1 of cycle 2.

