## **8.8 Duration of Study Treatment**

The expected duration of treatment for each subject is 4 cycles of treatment, each cycle lasting 4 weeks; with up to 4 weeks of rescreening for eligibility to continue on to subsequent cycles; followed by six additional months of ruxolitinib. The following may be reasons for removal from additional study treatment:

- unacceptable toxicity
- disease progression

- new GVHD (except grade I acute GVHD)
- prolongation of the most recent cycle to more than 8 weeks (for any reason)
- inadequate cell dose for further DLI
- consent is withdrawn or patient is not compliant

Patients who are unable to receive further DLIs after initial cycle(s), may continue to receive ruxolitinib as long as the physician believes they are benefiting from the treatment, the patient has not withdrawn consent, and they have not developed unacceptable toxicity.

All patients receiving at least one cycle of treatment will be followed per [Sections 11.1](#) and [11.2](#) and be evaluable per [Section 15](#).

Patients unable to continue DLI may be treated per physician's choice. These patients will still be followed per [Sections 11.1](#) and [11.2](#).

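### Section 6's four-infusion CD3 total for haploidentical donors (1.66) cannot share the basis of the sibling total (66); on that basis Table 4 gives 6.6

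*Combined protocol and SAP*

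**What the plan says.** Section 6 (Donors) sets a required CD3 total, in units of 10^8 cells per kg of recipient weight, which "for 4 DLI procedures is 66, 16.6, and 1.66 for matched sibling, matched unrelated, haploidentical donors, respectively". It does not say whether the totals are built from the bottom, middle or top of the permitted dose ranges.

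The doses themselves are in section 8.2 ("Table 4: DLI dose escalation algorithm"), and the Schema repeats the same numbers. Each infusion has a tenfold range that depends on donor type. Section 8.2 adds an escalation rule: "In the absence of new GVHD (any grade), the dose of DLI for the next cycle will be higher than the previous cycle". After new GVHD that still permits treatment, the dose is held.

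Cell supply is checked one infusion at a time:

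- Entry (5.1.5) asks for "Additional cells sufficient for the first DLI available from the same donor, or the donor must be willing to donate".
- Re-screening (8.5.2) accepts available cells or a willing donor, and adds: "If a sufficient number of cells for the next DLI is not available, patients will not receive further treatment on study".
- Section 4 covers a short collection: "If the collected cell dose in the DLI is less than the target dose, the patient will receive those collected cells and subsequently removed". The removal applies to later cycles; follow-up continues.
- Section 8.8 adds: "Patients who are unable to receive further DLIs after initial cycle(s), may continue to receive ruxolitinib".

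**The concern.** The three totals stand in one sentence and read as if computed in the same way. The sibling figure is exactly the sum of Table 4's upper ends and the unrelated figure is within 0.1 of it, but the haploidentical figure is about a quarter of it. The upper end of the fourth haploidentical infusion alone is 5, about three times the stated total for all four (5/1.66 = 3.0).

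What is at stake is narrow. Section 6 calls the figure required, and it is the only four-infusion quantity in the plan. A site that plans a single collection from a haploidentical donor would naturally take it as the target. If it is too low, a patient who tolerates three infusions could reach cycle 4 with too few cells for an in-range, escalated dose. That patient could then lose the cycle 4 decitabine and DLI (8.5.2), or receive a below-target last infusion (section 4).

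**Working it through.** **Inputs.** Table 4 of section 8.2, identical in the Schema (x10^8 CD3/kg):

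| | Sibling | Unrelated | Haploidentical |
|---|---|---|---|
| DLI #1 | 0.1-1 | 0.05-0.5 | 0.01-0.1 |
| DLI #2 | 0.5-5 | 0.1-1 | 0.05-0.5 |
| DLI #3 | 1-10 | 0.5-5 | 0.1-1 |
| DLI #4 | 5-50 | 1-10 | 0.5-5 |
| Stated total (section 6) | 66 | 16.6 | 1.66 |

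**Step 1: reproduce the stated totals.** Sum of upper ends:

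- Sibling: 1 + 5 + 10 + 50 = 66. Stated 66, exact.
- Unrelated: 0.5 + 1 + 5 + 10 = 16.5. Stated 16.6, 0.1 (0.6%) too high.
- Haploidentical: 0.1 + 0.5 + 1 + 5 = 6.6. Stated 1.66, not reproduced.

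The haploidentical gap is 6.6 - 1.66 = 4.94, and the ratio is 6.6/1.66 = 3.98.

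**Step 2: try other bases.** Each row gives sibling / unrelated / haploidentical.

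- Lower ends: 6.6 / 1.65 / 0.66.
- Arithmetic midpoints: 36.3 / 9.075 / 3.63.
- Geometric midpoints: 20.9 / 5.22 / 2.09.

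Holding the dose at one or more cycles, at upper ends, gives haploidentical totals of 0.4, 0.8, 1.2, 1.6, 1.7, 2.1 or 2.6. None is 1.66. The paths that give 1.6 and 1.7 give 16 and 17 for siblings, not 66.

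**Step 3: a check that does not depend on the basis.** The haploidentical/sibling ratio is 0.1 at all four steps and at both ends. Any rule that takes the same point in each range for both donor types must therefore give a haploidentical total of one-tenth of the sibling total: 0.1 x 66 = 6.6. The stated ratio is 1.66/66 = 0.025.

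**Step 4: what 1.66 can support.** Suppose exactly 1.66 is collected and the donor does not give again. The amount left for DLI #4 is 1.66 minus the sum of DLIs #1-3. It must be at least 0.5 (Table 4) and, with no new GVHD, higher than DLI #3 (section 8.2).

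| DLIs #1-3 | Used | Left | DLI #4 possible? |
|---|---|---|---|
| Upper ends: 0.1 + 0.5 + 1 | 1.6 | 0.06 | No: below 0.5 |
| 0.05 + 0.2 + 0.8 | 1.05 | 0.61 | In range, but not above 0.8, so not escalated |
| DLI #3 held at DLI #2: 0.1 + 0.5 + 0.5 | 1.1 | 0.56 | Table 4 minimum met |
| 0.05 + 0.1 + 0.5 | 0.65 | 1.01 | Yes: a dose of 1.0 brings the course to 1.65 |
| Lower ends: 0.01 + 0.05 + 0.1 | 0.16 | 1.5 | Yes |

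The Table 4 minimum is missed once DLIs #1-3 exceed 1.66 - 0.5 = 1.16. The second row shows that the escalation rule can fail below that figure.

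**The case against.** The strongest reply is that nothing in the conduct of the trial uses the four-infusion total. Doses come from Table 4. Entry and re-screening look only at the next infusion, and both accept a donor willing to give again. Section 8.2 allows a new unit, and section 4 deals with a short collection. All of this stands, and it is why the point is minor.

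A second reply is that the upper-end basis is inferred. Section 6 does not state it, and only one of the three figures matches it exactly. That also stands, but the one-tenth relation in step 3 needs no assumption about which point of the range was used.

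Two stronger readings are tempting, and the documents support neither.

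- **That 1.66 is impossible under Table 4.** It is not. It lies between the haploidentical minimum and maximum sums (0.66 and 6.6), is 2.5 times the minimum sum (1.66/0.66), and covers some escalating courses.
- **That the cause is a misplaced decimal point.** 1.66 is exactly one-tenth of 16.6, which invites that inference. Table 4 does not support that ratio: the haploidentical ranges are 0.2, 0.5, 0.2 and 0.5 of the unrelated ones. Another exact fit exists as well: 0.01 + 0.05 + 0.1 + 0.5 + 1 = 1.66 and 0.1 + 0.5 + 1 + 5 + 10 = 16.6. Those sums use five dose levels for four infusions and do not explain 66, so they settle nothing. They do show that a decimal shift is not the only candidate.

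**Conclusion.** The inconsistency is certain and its cause is not. As written, 66 and 1.66 cannot rest on one basis. If the sibling basis is the upper ends, the haploidentical total should be 6.6 (4.0-fold higher) and the unrelated total 16.5.

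The consequence is limited to collection planning. It takes a haploidentical recipient who reaches cycle 4, a site that collected only 1.66, earlier doses high enough to leave too little for an in-range, escalated DLI #4, and a donor who does not give again. The documents do not give the expected number of haploidentical recipients, so the frequency cannot be estimated. Such a patient may still continue ruxolitinib and would remain in follow-up.

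A reader might infer that haploidentical recipients will be under-dosed or the efficacy result biased. The documents do not support that: infused doses follow Table 4, and the primary analysis, sample size and error rates do not use the total. Nor do the documents show whether section 6 or Table 4 departs from what was intended.

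**What to change.** Ask the sponsor to confirm the haploidentical doses in Table 4.

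- If they are as intended, revise section 6 to say that its totals are the sums of Table 4's upper ends, and state 66, 16.5 and 6.6. This is a one-sentence correction with no change to design, data or analysis. Naming the basis matters because the new figure is a maximum, and a lower in-range course needs fewer cells.
- If they are not as intended, correct Table 4 and the Schema together, then recompute the section 6 totals from the corrected ranges. That would change permitted doses and so would be more than an editorial edit.

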## 7 Study Registration

To be eligible for registration to this study, the patient must meet all of the inclusion criteria and none of the exclusion criteria listed on the eligibility checklist based on the eligibility assessment documented in the patient's medical record.

The eligibility checklist for both the patient and donor will be completed at the time of study registration.

### 7.1 Registration with the University of Minnesota Clinical Trials Office

Upon completion of the screening evaluation, eligibility checklist and obtaining consent, the Site Study Coordinator or designee will enroll the patient and donor in OnCore. Complete registration information is found in the study's Procedures Manual for Affiliate Sites.

**Affiliate sites only:** At the time of registration, the signed consents will be uploaded into OnCore as an attachment under the appropriate record (patient or donor).

Affiliates are responsible for fulfilling any local registration requirements.

## **7.2 Patients Who Do Not Begin Study Treatment**

If a patient is registered to the study and is later found not able to begin study treatment (beginning with the ruxolitinib and decitabine); the patient will be removed from the study and treated at the physician's discretion. The study staff will update OnCore of the patient's non-treatment status (off study). The reason for removal from study prior to starting study treatment will be clearly indicated in OnCore. The patient will be replaced to complete enrollment.

## 8 Treatment Plan

In order to provide optimal patient care and to account for individual medical conditions, investigator discretion may be used in the prescribing of all supportive care drug therapy (i.e. acetaminophen, diphenhydramine, G-CSF, antimicrobials, etc.).

**Table 1: Ten Day Dosing Schedule**

Treatment	Cycle 1			Between Cycles	Cycles 2 -4			Month 1 – 6 after end of final cycle
	Day 1-10	Between Day 11-21	Day 22-28	Day 29 - 56	Day 1-10	Between Day 11-21	Day 22-28	
Decitabine	1X daily				1X daily			
DLI		Once per dose algorithm*				Once per dose algorithm*		
Ruxolitinib	2x daily							→
Rescreen for eligibility				Continuous rescreening per section 8.5				

\*See [section 8.2, Table 4](#): DLI dose escalation algorithm

The expected duration of treatment for each subject is 4 cycles of treatment, each lasting 4-8 weeks. As soon as continued eligibility for a subsequent cycle is confirmed after a given cycle, the subsequent cycle will start. Days 29-56 provide a window to start the next cycle and can be used to allow for resolution of toxicities. Refer to [Sections 11.1](#) and [11.2](#) for the schedule of clinical and research related evaluations and procedures, and [section 11.3](#) for the schedule of donor evaluations. Decitabine schedule: 10 days ([Table 1](#)) or 5-2-5 ([Table 2](#)) will be per institution, physician, or patient preference. If a CR is achieved after 2 cycles using the 10-day schedule, subsequent cycles will change to a 5 day schedule (see [Table 3](#)).

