**Table 2: Alternative Ten Day Dosing Schedule**

Treatment	Cycle 1			Between Cycles	Cycles 2 -4			Month 1 – 6 after end of final cycle
	Day 1-5 and 8-12	Between Day 13-22	Day 23-28	Day 29 - 56	Day 1-5 and 8-12	Between Day 13-22	Day 23-28	
Decitabine	1X daily				1X daily			
DLI		Once per dose algorithm*				Once per dose algorithm*		
Ruxolitinib	2x daily							→
Rescreen for eligibility				Continuous rescreening per section 8.5				

\* See [section 8.2, Table 4](#): DLI dose escalation algorithm

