**Table 3: Five Day schedule for Cycles 3 and 4 if CR is achieved after Cycle 2**

Treatment	Cycle 3		Between Cycles	Cycle 4		Month 1 – 6 after end of final cycle
	Day 1-5	Between Day 6 - 16	Day 17 - 56	Day 1-5	Between Day 6-16	
Decitabine	1X daily			1X daily		
DLI		Once per dose algorithm*			Once per dose algorithm*	
Ruxolitinib	2x daily					→
Rescreen for eligibility			Continuous rescreening per section 8.5			

\* See [section 8.2, Table 4](#): DLI dose escalation algorithm

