#### Acute Graft-Versus-Host Disease

Infusion of donor lymphocytes into patients who relapse post allogeneic bone marrow transplantation has frequently resulted in development of acute graft-versus-host disease with involvement of the skin and liver, often requiring treatment. Despite treatment, some cases of GVHD have been of high grade and deaths from GVHD have been reported. GVHD may occur between 1 and 24 weeks post-infusion of the donor lymphocytes. Patients will have regular assessment for development of new or worsening of existing GVHD during the entire study period.

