Required prior to cycle 3. This sample will not be taken if not moving on to cycle 3.

Day 1-5 in cycle 3 and 4 if CR achieved;

Between day 6 and 16 in cycle 3 and 4 if CR achieved

 Day 1 of cycle and additional frequency per site institutional guidelines for clinical care. If screening (baseline) labs were performed within 7 days of Day 1 of treatment, these do not need to be repeated. For cycle 2 and later, lab work may be performed up to 3 days prior to the day 1 treatment day.

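### Table 1, Table 3 and part of the 11.1 calendar allow DLI one day past the 10-day rule, and Table 3's between-cycle column from day 17 contradicts the 4-week cycle

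*Combined protocol and SAP*

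**What the plan says.** **DLI window in the text.** Section 8.2 has DLI given "Within 10 days after the last dose of decitabine in each cycle". Section 4 states the same rule ("DLI from the original donor will be infused within 10 days after the last dose of decitabine in each cycle"), as does the Synopsis. Section 8.1 puts the last decitabine dose on day 10 (10-day schedule), day 12 (5-2-5 schedule) or day 5 (5-day schedule, cycles 3 and 4 after a CR).

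**DLI window in the tables and calendar.**
- Table 1, 10-day schedule: "Between Day 11-21". The 11.1 calendar repeats 11-21.
- Table 2, 5-2-5 schedule: "Between Day 13-22". The 11.1 calendar repeats 13-22.
- Table 3, 5-day schedule: "Between Day 6 - 16". Footnote 7 of 11.1 reads "Between day 6 and 16 in cycle 3 and 4 if CR achieved".

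**Start of the next cycle.** The text below Table 1 in Section 8 says "Days 29-56 provide a window to start the next cycle". Section 8 gives cycles of 4 to 8 weeks, and Section 8.8 gives 4-week cycles followed by up to 4 weeks of rescreening. Tables 1 and 2 and the 11.1 calendar all use day 29-56 for the between-cycle period. Table 3 labels day 17 to day 56 as between cycles and shows rescreening there. Its Cycle 4 block ends with the day 6-16 DLI column and passes directly to the months after the final cycle.

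**Escalation.** Under 8.2 the next DLI dose is higher unless there has been new GVHD of any grade. Under 8.5.6 new GVHD other than grade I acute GVHD ends further cycles. Section 9.3 says "GVHD may occur between 1 and 24 weeks post-infusion of the donor lymphocytes".

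**The concern.** These are dosing rules that sites apply directly, and they disagree. A DLI on day 21 of the 10-day schedule, or on day 16 of the 5-day schedule, follows the table and calendar but departs from 8.2.

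The column in Table 3 matters more. Section 8 has the next cycle start as soon as continued eligibility is confirmed. Section 8.5 caps a cycle at 8 weeks, but no section sets a minimum interval between DLIs, and no marrow is required before cycle 4. Nothing in Table 3 itself would hold a site back until day 29. The transition affected is DLI #3 to DLI #4, the two highest dose rows of Table 4, where the dose rises 5-fold (matched sibling and haploidentical donors) or 2-fold (matched unrelated donors). That rise depends on there being no new GVHD, which is informative only if GVHD from DLI #3 has had time to appear.

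Table 3 also leaves the end of the final cycle unclear: day 16 as drawn, or day 28 under a 4-week cycle, a difference of 28 − 16 = 12 days. The post-cycle ruxolitinib period, the follow-up visits, the 90- and 180-day samples and the end of the grade III-IV aGVHD stopping-rule window are all counted from the last cycle.

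**Working it through.** **Step 1: window implied by the 10-day rule.** The first day is the last decitabine day + 1, and the last day is the last decitabine day + 10.

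| Schedule | Last decitabine day | Implied window | Window in table | Last table day minus last decitabine day |
|---|---|---|---|---|
| 10-day (Table 1, 11.1) | 10 | 11-20 | 11-21 | 11 |
| 5-2-5 (Table 2, 11.1) | 12 | 13-22 | 13-22 | 10 |
| 5-day (Table 3, footnote 7) | 5 | 6-15 | 6-16 | 11 |

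Table 2 reproduces the rule exactly. The other two run one day over. No single way of counting days reconciles all three.

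**Step 2: shortest DLI-to-DLI gap.** Gap = (start day of next cycle − 1 + first DLI day of that cycle) − last DLI day of current cycle.

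Cycle 3 to cycle 4 on the 5-day schedule:
- Table 3 taken alone, DLI on day 16, cycle 4 from day 17: (17 − 1 + 6) − 16 = 6 days.
- Same start, but the 10-day rule kept (DLI on day 15): (17 − 1 + 6) − 15 = 7 days.
- Start on day 29, DLI on day 16: (29 − 1 + 6) − 16 = 18 days.
- Start on day 29, DLI on day 15: (29 − 1 + 6) − 15 = 19 days.

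The earliest start differs by 29 − 17 = 12 days.

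**Step 3: other transitions, all with a day 29 start.**
- 10-day to 10-day: (28 + 11) − 21 = 18, or (28 + 11) − 20 = 19 days.
- 5-2-5 to 5-2-5: (28 + 13) − 22 = 19 days.
- 10-day cycle 2 to 5-day cycle 3: (28 + 6) − 21 = 13, or (28 + 6) − 20 = 14 days.
- 5-2-5 cycle 2 to 5-day cycle 3: (28 + 6) − 22 = 12 days.

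The switch to the 5-day schedule therefore shortens the gap to 12-14 days even when every cycle starts on day 29.

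**Step 4: comparison with GVHD onset.** The onset range in 9.3 begins at 1 week. A 6-day gap falls before it and a 7-day gap falls at its lower limit. Gaps of 12 to 19 days fall inside the range, and no cycle length in this protocol clears its 24-week upper end.

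**The case against.** A reader might infer that a fully compliant site may give escalating DLIs 6 days apart. The documents do not support this. Starting cycle 4 on day 17 makes cycle 3 16 days long, which breaks the 4-week minimum in the Synopsis, Section 4, Section 8 and Section 8.8, and also the day 29-56 start window. The 11.1 calendar, whose footnotes expressly cover the 5-day schedule, also places between-cycle assessments on day 29-56. A site following the whole protocol has a minimum gap of 18-19 days from DLI #3 to DLI #4. The 6-day figure also needs both slips together.

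Table 3 has a harmless reading too: it may simply merge the rest of the cycle with the between-cycle period. No sentence says that a cycle may start on day 17. The Cycle 4 block weakens that reading, because it has no column after day 16, where Tables 1 and 2 keep day 22-28 or day 23-28.

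The one-day overrun is small, and nothing in the protocol suggests that a single day affects safety or the endpoint. The ±3 days in Section 11 is written for scheduled evaluations and does not clearly extend to the infusion.

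These points limit the scope of the finding. The contradictory instructions remain.

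**Conclusion.** The plan is inconsistent as written, and the inconsistency is narrow.

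- The DLI window is one day too long in Table 1, in the 11-21 entry of 11.1, in Table 3 and in footnote 7. Table 2 and the 13-22 entry are correct.
- Table 3's between-cycle column and its Cycle 4 block contradict the 4-week cycle and the day 29 start. A site using that table alone could give DLI #4 6 or 7 days after DLI #3, against the 18-19 days that the rest of the protocol implies.
- Only this one transition is affected, and only in patients in CR after cycle 2 who remain eligible for cycle 4.

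The 6- and 7-day figures assume that the site takes Table 3 literally, confirms eligibility at once and uses the last permitted DLI day followed by the first. They are limits, not expected practice. The 6-month OS comparison, alpha, power and sample size do not depend on any of this. The case for correction is dosing clarity at the highest DLI doses, at almost no cost.

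**What to change.** 1. Change the DLI window to day 11-20 in Table 1 and 11.1, and to day 6-15 in Table 3 and footnote 7. The late-cycle column of Table 1 then becomes day 21-28. If 11 days was intended, amend the Synopsis, Section 4 and 8.2 instead, and move Table 2 and its 11.1 entry to day 13-23 (12 + 11 = 23).
2. In Table 3, add a day 16-28 column to both cycles (day 17-28 under an 11-day rule) and set the between-cycle column to day 29-56. This also fixes the end of the final cycle at day 28 if no delay occurs.
3. Ask the clinical team whether to state a minimum interval between DLIs. Steps 1 and 2 alone still leave a 12-14 day gap when a 10-day or 5-2-5 cycle 2 is followed by a 5-day cycle 3. The length of any minimum is a clinical decision.

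The cost is a few table headers, one calendar entry and one footnote in the next amendment, plus one sentence if a minimum interval is adopted. No visits or patients are added.
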